	
The PK population includes all subjects in the Safety Population who have at least 1 plasma sample with quantifiable concentration. The PK population will be used to summarize all PK endpoints.
 
The following populations are planned for the OLE of this study:
 
The OLE Safety population: all subjects who complete the 12-week Double-blind Treatment Period and receive at least 1 application of study drug in the OLE.
 
OLE ITT population: all subjects who complete the 12-week Double-blind Period and who sign the OLE informed consent.
 
The OLE mITT population: all subjects in the OLE safety population with at least 1 assessment of efficacy after Visit 6.
 
The OLE PP population: all subjects in the OLE mITT population who met all inclusion criteria and no exclusion criteria, were compliant with study drug application from baseline through EOT, and who had no significant protocol deviations throughout the study.
 
Subject Characteristics and Disposition: Descriptive statistics will be used to summarize demographic characteristics (age, sex, ethnicity, and race) and baseline characteristics for all enrolled subjects. Medical history, physical examination findings, and vital sign measurements for all randomized subjects will be presented in listings.
 
Efficacy Analyses: The number and proportion of subjects in each treatment group with successful resolution of LI by Week 12/EOT in the Double-blind Period will be presented. The primary efficacy endpoint will be analyzed using a logistic regression model with treatment and age group as factors. Other baseline characteristics and interactions may be included. The odds ratios and 95% CIs for the odds ratios will be presented. The difference in proportions between the active trifarotene cream HEI and vehicle cream groups, 95% CIs for the differences, and P-values for the differences in treatment will also be presented.
 
The IGA scores as well as secondary and exploratory efficacy endpoints will be analyzed by visit using descriptive statistics through Week 24. Change from Baseline through Week 12 will be presented and analyzed using a mixed model for repeated measures (MMRM). The model will include the change from Baseline score as the dependent variable, treatment group as a fixed effect, subject as a random effect, and Baseline score value as a covariate. Frequencies of results and 95% confidence intervals will also be reported, and scores will be analyzed as categorical variables using the Cochran-Mantel-Haenszel test. For subjects who report having fissures, the number of fissures and pain related to fissures will also be presented on a scale of 0-3 (none, mild, moderate, severe).
 
Clinical Pharmacology Analyses: Noncompartmental PK analysis will be performed for the PK subset of subjects, as data permit. Plasma concentrations of CD5789 and its major metabolites will be measured and will be listed by subject.
 
Safety Analyses: Safety and tolerability will be assessed based on the incidence of reported TEAEs, and SAEs, including relationship to study drug and severity, as well as physical examination findings, vital sign measurements (supine systolic blood pressure [SBP] and diastolic blood pressure [DBP] and pulse), clinical laboratory results (hematology, including serum aminotransferases and serum lipids, coagulation, clinical chemistry, and urinalysis) and 12-lead ECGs. Descriptive statistics for observed values and change from Baseline will be calculated at each visit within each study period and by treatment group within cohort.

--	---

SAMPLE SIZE DETERMINATION	The first cohort of 15 subjects is a reasonable sample size to assess safety and tolerability before enrolling additional subjects in Cohort B. Accounting for a 20% drop-out/nonevaluable rate, a total sample size of 120 subjects randomized in a 1:1:1 ratio to 2 active trifarotene cream HE1 arms and a vehicle cream arm will provide >80% power to detect a difference between each separate trifarotene cream HE1 arm (32 evaluable subjects) and the vehicle cream arm (32 evaluable subjects) 2-sided Fisher's Exact Test assuming a 70% success rate and a 40% success rate, respectively. This study is not powered to detect a difference between the 2 active arms.
STUDY AND TREATMENT DURATION	
The sequence and maximum duration of the study will be as follows:
 
 1. Screening: Up to 35 days (after signing informed consent, if necessary, washout may be up to 3 months, and subjects should return to the site after washout to complete the study eligibility requirements). 2. Double-blind study drug application: Twice weekly for up to 12 weeks. 3. Optional Open-label Extension: Twice weekly for up to 12 weeks. 4. Follow-up: 14 days after last study drug application. 
The maximum study duration for each subject is approximately 229 days (33 weeks).
 
The maximum treatment duration for each subject is 24 weeks.

2.2. Schedule of Events

Table 2-1: Schedule of Events for Double-blind Period

	Screening (-35 days to -1 day) Washout up to 3 months ^a	Double-blind Treatment Period						
		Baseline (Day 1)	Telephone Visit (Day 7)	Day 14 ± 5 days	Day 30 ± 7 days	Telephone Visit (Day 45)	Day 60 ± 7 days	Day 90 ^{b,c} ± 7 days (ET)
Visit	1	2		3	4		5	6
Week		1		2	4		8	12
Written informed consent	X							X ^a
Assign screening number	X							
Inclusion/exclusion criteria	X	X						
Demographics	X							
Medical history	X							
Physical examination	X	X ^d						X ^c
Vital signs (blood pressure and pulse)	X	X		X	X		X	X
Height, weight, and BMI	X							X
IGA assessment ^e	X	X		X	X		X	X
VIIS ^f assessment	X	X		X	X		X	X
Roughness assessment ^g	X	X		X	X		X	X
Palm/sole assessment	X	X		X	X		X	X
Palm/sole fissuring assessment ^h	X	X		X	X		X	X
Ectropion score	X	X		X	X		X	X
Photographs ⁱ		X			X			X
Quality of life per Dermatology Life Quality Index (DLQI)		X		X	X		X	X

	Screening (-35 days to -1 day) Washout up to 3 months ^a	Double-blind Treatment Period						
		Baseline (Day 1)	Telephone Visit (Day 7)	Day 14 ± 5 days	Day 30 ± 7 days	Telephone Visit (Day 45)	Day 60 ± 7 days	Day 90 ^{b,c} ± 7 days (ET)
Visit	1	2		3	4		5	6
Week		1		2	4		8	12
EQ-5D Quality of Life Questionnaire		X		X	X		X	X
12-lead ECG ^l	X	X			X			X
Clinical laboratory tests (hematology, chemistry, urinalysis) ^k	X	X			X			X
Serology (hepatitis B surface antigen, hepatitis C)	X							
Pregnancy test for female subjects (serum at Screening; urine subsequently)	X	X			X		X	X
Randomization via IWRS		X						
PK blood sample collection ^l		X		X	X		X	X
Initial study drug application by clinic staff and measurement ^m		X						
Application instructions, advice on emollient and sunscreen use		X	X	X	X	X		
Dispense study drug and diaries ⁿ		X ⁿ		X	X		X	
Concomitant medications	X	X	X	X	X	X	X	X
Tolerability assessment		X		X	X		X	X
Adverse events (and review diaries)		X	X	X	X	X	X	X
Collect all used/unused study drug ^o				X	X		X	X
Provide information about OLE option					X	X	X	

Abbreviations: BMI = body mass index; DLQI = Dermatology Life Quality Index; ECG = electrocardiogram; ET = early termination; HEENT = head, eyes, ears,

nose, throat; ICF = informed consent form; IGA = Investigator's Global Assessment; IWRS = interactive web response system; OLE = open-label extension; PK = pharmacokinetic; WOCBP = women of childbearing potential; VIIS = Visual Index for Ichthyosis Severity

- a. Upon signing informed consent and entering the Screening Period, subjects will stop using physical and medical treatments for LI, including balneotherapy, and may begin to washout prohibited topical and systemic treatments with designated washout periods, as applicable. Washout may be up to 3 months, as necessary. During washout, subjects may continue taking usual care of visible skin (face and scalp) for cosmetic reasons and of extremities (hands and feet) to avoid functional consequences on walking or moving their fingers. Subjects may shower, but not bathe or swim during the Screening Period. After completing any necessary washout of prohibited medications, subjects will return to the site to complete the study eligibility requirements.
- b. Day 90 procedures should be conducted for subjects who terminate the study early. If a subject discontinues IP, but continues to attend clinic visits, Day 90 will occur as scheduled. Day 90/Week 12 will be the first visit of the OLE for subjects who choose to continue (subjects will have up to 7 days to decide to sign the ICF and begin the OLE). Subjects who decide to continue into the OLE will have the following additional procedures: 1) sign informed consent; 2) will be weighed; 3) will be instructed on study drug application; 4) will be given new diaries, and 5) will be provided with study drug.
- c. A Follow-up telephone call will be made within 14 days after Day 90 to subjects who choose not to continue into the OLE.
- d. Limited physical examination to include HEENT, cardiorespiratory, abdomen, range of motion.
- e. IGA: 0 = clear; 1 = almost clear; 2 = mild; 3 = moderate; 4 = severe.
- f. VIIS scale for each body area: chest/abdomen, back, legs, and arms, for a possible overall score = 16.
- g. Roughness (0-4 scale);
- h. Palm/sole fissuring assessment: present/absent/number/pain (0-3 scale).
- i. Photography will be performed at sites with the capability for subjects who sign a photographic ICF. A central reader who will not be an investigator in the study will review the photographs to assess consistency of investigator scoring of LI severity as a quality check.
- j. ECG to be conducted at Screening, Baseline, Day 30, and Day 90 for all subjects. Subjects in the PK substudy will also have postdose ECGs at each serial blood draw on Day 1 and Day 30.
- k. Subjects must be fasting (i.e., at least 8 hours)
- l. Samples for PK will be drawn from all subjects at Baseline and at each clinic visit. At selected sites among subjects who consent to participate in the PK substudy, samples will be taken predose and at 1, 2, 4, 8, 12, and 24 hours postdose on Day 1. On Day 30, IP will be applied in the clinic for PK substudy subjects, and PK samples will be taken predose and at 1, 2, 4, 8, 12, and 24 hours postdose. Trough levels will be drawn when the subjects are in the clinic for other study visits (i.e., Day 14, Day 60, and Day 90). Visits for PK must occur at least 24 hours after the last application of the IP to avoid contamination of the blood samples with any IP that may have remained in the skin after the last application.
- m. Study staff will apply initial dose of study drug in the clinic after Baseline measurements, and the amount of study drug used will be measured (i.e., 36-g tube will be measured before and after application to determine amount used) to determine fixed dose.
- n. Study drug provided in 50-g tubes (maximum single application is 36 g). Measure study drug tubes before dispensing; subjects must record days/times of study drug application in the diaries and any areas of skin not treated, e.g., due to local reactions). Dispense enough additional study drug until next visit (except at Day 90, unless subject consents to continue into OLE).
- o. Confirm study drug compliance by measuring tube weight and reviewing diary.

Table 2-2: Schedule of Events for Open-label Extension

	Open-label Treatment Period						Follow-up
	Telephone Visit (Day 97) ^a	Day 104 ± 5 days	Day 120 ± 7 days	Telephone Visit (Day 134)	Day 150 ± 7 days	Day 180 ± 7 days/ET	Day 194 or 14 days after End of Open-label Treatment
Visit		7	8		9	10	11
Week		14	16		20	24	26
Informed consent ^a							
Physical examination ^b						X	X
Vital signs (blood pressure and pulse)			X	X		X	X
Weight	X						
Record IGA ^c		X	X		X	X	X
VIIS ^d assessment		X	X		X	X	X
Roughness assessment ^c		X	X		X	X	X
Palm/sole assessment		X	X		X	X	X
Palm/sole fissuring assessment		X	X		X	X	X
Ectropion score			X	X		X	X
Clinical laboratory tests (hematology, chemistry, urinalysis) ^f			X			X	
Pregnancy test for female subjects (urine)			X		X	X	X
ECG			X			X	
PK blood sample collection ^g			X			X	
Application instructions, advice on emollient and sunscreen use ^h	X	X	X	X			

	Open-label Treatment Period						Follow-up
	Telephone Visit (Day 97) ^a	Day 104 ± 5 days	Day 120 ± 7 days	Telephone Visit (Day 134)	Day 150 ± 7 days	Day 180 ± 7 days/ET	Day 194 or 14 days after End of Open-label Treatment
Visit		7	8		9	10	11
Week		14	16		20	24	26
Dispense study drug and diaries ⁱ		X	X		X		
Concomitant medications	X	X	X	X	X	X	X
Tolerability assessment		X	X		X	X	
Adverse events (and review diaries)	X	X	X	X	X	X	X
Collect all used/unused study drug ^j		X	X		X	X	

Abbreviations: ECG = electrocardiogram; ET = early termination; HEENT = head, eyes, ears, nose, throat; ICF = informed consent form; IGA = Investigator's Global Assessment; PK = pharmacokinetic; OLE = open-label extension; VIIS = Visual Index for Ichthyosis Severity; WOCBP = women of childbearing potential

- Subjects will sign the OLE ICF at the Double-blind Day 90/Week 12 Visit or within 7 days thereafter. All efficacy assessments, safety/tolerability assessments, including clinical laboratory testing and PK from Day 90/Week 12 will be carried over for the OLE and will not be repeated.
- Limited physical examination to include HEENT, cardiorespiratory, abdomen, range of motion.
- IGA: 0 = clear; 1 = almost clear; 2 = mild; 3 = moderate; 4 = severe
- VIIS scale for each body area: chest/abdomen, back, legs, and arms, for a possible overall score = 16.
- Roughness (0-4 scale); fissuring assessment on palms/soles: present/absent/number/pain (0-3 scale).
- Subjects must be fasting (at least 8 hours)
- Samples for PK will be drawn from all subjects at Day 120 and Day 180. Visits for PK must occur at least 24 hours after the last application of the IP to avoid contamination of the blood samples with any IP that may have remained in the skin after the last application.
- Subjects must record days/times of study drug application in the diaries and any areas of skin not treated (e.g., due to local reactions).
- All subjects in the OLE will receive trifarotene 200 µg/g. Study drug provided in 50-g tubes (maximum single application is 36 g). Measure study drug tubes before dispensing. Dispense enough additional study drug until the next visit (except at Day 180).
- Confirm study drug compliance by measuring tube weight and reviewing diary.

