
Local tolerability may differ in subjects with LI compared to healthy subjects, as their skin is drier and may be more sensitive. Local tolerability will be followed very carefully during the study. Subjects will receive information on study drug use and stopping rules and will be instructed to contact the site with any safety/tolerability issues. Study personnel will telephone subjects in between scheduled visits (i.e., at Day 7 and Day 45 in the Double-blind Period; at Day 97 and 134 in the OLE) to assess safety; an unscheduled clinic visit may be performed, if necessary. If the treatment causes application site reactions, the frequency of application will be reduced or interrupted only on the area of concern, as indicated herein. During all clinic visits, the investigator will assess local tolerability (Scale: 0-3 [none, mild, moderate, severe]) for stinging/burning, pruritus, erythema) for each body area (chest/abdomen, back, arms, legs, and face/neck), and the following procedures will be followed:
 
 - If a score of 2 (moderate) is recorded on a local tolerability assessment scale (stinging/burning, pruritus, erythema) on any treated area, the study drug will be applied on that area only once weekly, until the score is back to <2. Continue to treat all other areas twice weekly provided the score is <2 on those areas. - If a score of 3 (severe) is recorded on a local tolerability assessment scale (stinging/burning, pruritus, erythema) on any treated area, the study drug will not be applied on that area until the score is back to <3 (i.e., “drug holiday”). Continue to treat all other areas twice weekly provided the score is <2 on those areas. 
Stopping rules and treatment modification will be defined at the subject level based on local tolerability, selected laboratory parameters, and adverse events (AEs). Any changes in dosing must be documented in the subject diary and the electronic case report form.
 
All subjects will be provided with diaries in which to record study drug application (days/times and any areas of skin not treated [e.g., due to local reactions]) and any AEs, including application site reactions and concomitant medications used. Subjects will also be advised on permitted emollient(s) use on nontreatment days during the study; use of emollient(s) and/or sunscreen(s) on study drug treatment days within 4 hours before or after study drug application is prohibited.
 
At all sites with photographic capability, photographs will be taken as source data to support scoring at Baseline, Day 30, and Day 90. A central reader who will not be an investigator in the study will review the photographs to assess consistency of investigator scoring of LI severity as a quality check. Photographs may also be used for scientific publication purposes. Subjects will sign a separate, optional photographic informed consent form (ICF).
 
Samples for pharmacokinetic (PK) analysis will be drawn from all subjects at Baseline and at each clinic visit. Visits for PK must occur at least 24 hours after the last application of the IP to avoid contamination of the blood samples with any IP that may have remained on the skin after the last application. Subjects should not apply IP on visit days until after the visit.
 
In addition, a PK substudy will be conducted on Days 1 and 30 at sites with the capability to conduct it. Participation in the PK substudy will be optional and will include at least 30 subjects. Subjects who participate in the PK substudy will come from both study cohorts and will undergo serial blood sampling predose and at 1, 2, 4, 8, 12, and 24 hours postdose on Day 1 and Day 30. Trough levels will be drawn for these subjects at each of the other clinic visits. For the subjects in the PK substudy, postdose ECGs will be performed at each serial blood draw on Day 1 and Day 30.
 
Subjects who complete the Double-blind Treatment Period will have the option to continue into the OLE to assess safety for an additional 12-weeks with trifarotene cream HE1 200 µg/g twice weekly, on up to 90% of BSA, sparing the scalp, inguinal, and axillary areas. Subjects with heavy facial hair should not apply IP to hair-bearing areas. During the OLE, subjects will return to the site at Weeks 14, 16, 20, 24, and 26 for safety,

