9.2. Treatments Administered

For the Double-blind Treatment Period, a fixed dose (determined at Visit 2) of trifarotene cream HE1 100 µg/g or 200 µg/g or vehicle cream will be applied topically twice weekly on up to 90% BSA of each subject. The IP should be applied thinly and gently rubbed in.

Study staff will apply the first administration of IP in the clinic on Day 1 after Baseline measurements, and the amount of IP used will be measured (i.e., 50-g tube will be measured before and after application to determine amount used). If the product will be applied at home by someone other than the study subject, it is recommended that this person assist with application at the first visit to learn how the IP is applied.

The maximum dose per application is 36 g (i.e., 1 tube). Subjects will receive an adequate number of tubes to use 1 tube per application and will use a new tube for each treatment day. Subjects may use less than full amount of product in a tube. Subjects will continue treatment for up to 12 weeks.

After the Day 1 visit, subjects will apply approximately the same amount (up to 36 g) of study drug as for the first dose on up to 90% of BSA twice weekly, sparing the scalp, inguinal, and axillary areas. Subjects with heavy facial hair should not apply IP to hair-bearing areas. Persons other than the study subject applying the study drug must wash their hands after application or use disposable vinyl gloves. In addition, a long-handled applicator will be provided for application on the back. The applicator must be washed with warm water and soap after every application.

Trifarotene cream should not come into contact with the eyes, mouth, angles of the nose, or mucous membranes. For the ectropion treatment, Q-tips are recommended for precise application on eyelids, without contact to the eye or conjunctiva. If the IP gets into the eye, it must be flushed immediately with warm water. In case of eye irritation, the subject must be seen by an ophthalmologist.

For the OLE, all subjects will receive trifarotene cream HE1 200 µg/g and apply the same fixed dose in the same manner as in the Double-blind Period for an additional 12 weeks.

Visits for PK must occur at least 24 hours after the last application of the IP to avoid contamination of the blood samples with any IP that may have remained in the skin after the last application.

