10.2.2.7 Visit 6 (90 ±7 days) or Early Termination

The following procedures will be performed on Day 90 in the study clinic:

1. Record responses to DLQI and EQ-5D Quality of Life Questionnaires.
2. Perform a physical examination.
3. Record vital signs (blood pressure and pulse).
4. Record concomitant medications and concomitant therapies.
5. Record IGA.
6. Record VIIS.
7. Record roughness assessment.
8. Record palm/sole assessment.
9. Record palm/sole assessment of fissuring.
10. Record ectropion score.
11. At sites where the optional photographic substudy is conducted, take photographs of subjects who have provided informed consent for the substudy.
12. Assess local tolerance.
13. Record AEs and review diary.
14. Perform a 12-lead ECG.
15. Perform a urine pregnancy test for WOCBP.
16. Collect blood and urine for routine laboratory tests (subject must be fasting at least 8 hours).
17. Collect a PK blood sample (all subjects).
18. Collect returned study drug tubes; confirm study drug compliance by weighing returned tube contents and reviewing diaries.

For subjects who successfully complete (i.e., have reliable visit attendance and compliance with IP application, in the investigator's opinion) the initial 12 weeks of double-blind treatment and choose to continue into the OLE, this visit will be the first visit of that portion of the study. All efficacy assessments, safety/tolerability assessments, including clinical laboratory testing, PK from Day 90/Week 12 will be carried over to the OLE and will not be repeated. Subjects will have up to 7 days to decide to enter the OLE; if the subject chooses to continue into OLE, the following additional procedures will be done:

1. Have the subject sign OLE-specific informed consent.
2. Measure subject's weight.
3. Instruct subject on study drug application, and advise subjects regarding permitted emollient(s) and/or sunscreen for use on nontreatment days; use of emollient(s) on study drug treatment days within 4 hours before or after study drug application is prohibited. Remind subjects that at least 24 hours must have elapsed since IP application before the

PK draws at the Week 16 and Week 24 Visits, and not to apply IP on visit days until after the visits.

4. Weigh new study drug tubes and dispense enough additional study drug until next visit (only for subjects who choose to continue into the OLE).
5. Dispense study diary.

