10.2.4.1 Telephone Visit (Day 97)

Clinic staff will telephone subject to assess safety (AEs) and to record concomitant medications/therapies. Staff will instruct subject on study drug application, advise subjects regarding permitted emollient(s) for use on nontreatment days (use of emollient(s) on study drug treatment days within 4 hours of study drug application is prohibited), and remind subjects not to apply IP on visit days until after the visit. An unscheduled clinic visit may be performed, if necessary.

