10.2.4.2 Visit 7 (Week 14; Day 104 ± 5 days)

The following procedures will be performed at this study clinic visit:

1. Record concomitant medications and concomitant therapies.
2. Record vital signs (blood pressure and pulse).
3. Record IGA.
4. Record VIIS.
5. Record assessment of roughness.
6. Record palm/sole assessment.
7. Record palm/sole assessment of fissuring.
8. Record ectropion score.
9. Assess and record local tolerance/AEs and review diary.
10. Collect returned study drug tubes; confirm study drug compliance by weighing returned tube contents and reviewing diaries.

11. Weigh new study drug tubes and dispense enough additional study drug until next visit, and new diary.
12. Instruct subject on study drug application, and advise subjects regarding permitted emollient(s) for use on nontreatment days; use of emollient(s) and/or sunscreen on study drug treatment days within 4 hours before or after study drug application is prohibited. Remind subjects that 24 hours must have elapsed since IP application before the subject's next visit. Subjects should not apply IP on visit days until after the visit. at the Week 16 and Week 24 Visits, and not to apply IP on visit days until after the visit.

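### The first OLE safety call is fixed at Day 97 rather than timed from the OLE start, so a subject who takes the permitted 7 days to decide can be called on or before the day open-label treatment begins.

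*Protocol*

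**What the plan says.** All schedule references are to Amendment 2, the latest version whose tables are in the file.

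Table 2-1 footnote b treats Day 90/Week 12 as the first OLE visit but adds that "subjects will have up to 7 days to decide to sign the ICF and begin the OLE". Table 2-2 footnote a repeats this: "Subjects will sign the OLE ICF at the Double-blind Day 90/Week 12 Visit or within 7 days thereafter". Section 10.2.2.7 says the same: "Subjects will have up to 7 days to decide to enter the OLE". Visit 6 has a window of ±7 days.

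Drug supply depends on consent. Table 2-1 footnote n reads "Dispense enough additional study drug until next visit (except at Day 90, unless subject consents to continue into OLE", and Section 10.2.2.7 lists consent, weighing, instruction, drug and diary as steps for subjects who choose to continue.

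The first OLE call is set at Day 97 without a window (Table 2-2 and Section 10.2.4.1). The Synopsis gives its purpose: "at Day 97 and 134 in the OLE) to assess safety". Section 10.2.4.1 describes it as follows: "Clinic staff will telephone subject to assess safety (AEs) and to record concomitant medications/therapies". Visit 7 is set at Day 104 ±5. Both dates are study days counted from double-blind Day 1. Neither is restated relative to the start of open-label treatment.

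The double-blind period differs, because its first dose is fixed. Section 9.2 states: "Study staff will apply the first administration of IP in the clinic on Day 1 after Baseline measurements".

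**The concern.** The call's date does not move when the OLE start moves. A subject can follow the protocol exactly and still be called before there is any open-label exposure to ask about.

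This matters because Section 11.3.1 makes local application-site reactions events of special interest on the ground that they cluster at the start of retinoid treatment. OLE entry is such a start for two of the three arms. Former vehicle subjects receive their first trifarotene of the study, at the higher strength, and 100 µg/g subjects step up to 200 µg/g. Subjects from the 200 µg/g arm have no dose step.

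The dose reductions in Section 9.4 follow from scores recorded at clinic visits. The call is therefore the scheduled opportunity to find a problem before Visit 7 and bring the subject in. Placed on or before the start, it keeps its instruction and medication-recording functions but loses this one.

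**Working it through.** **Inputs.** Visit 6 on day v, from 83 to 97 (Day 90 ±7). Decision days d, from 0 to 7. Call on Day 97. Visit 7 window Day 99 to 109 (Day 104 ±5). Screening 35 days and follow-up 14 days (Section 10.1.1). Last OLE treatment visit on Day 180.

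**The plan's own total.** 35 + 180 + 14 = 229 days, or 32.7 weeks, which matches the stated maximum of about 229 days (33 weeks). The match requires that no gap lies between Visit 6 and the OLE start. The calendar was therefore built on a Day 90 start, although the text permits a later one.

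**Offsets.** OLE start s = v + d. Call offset = 97 − s. Visit 7 offset = (99 to 109) − s.

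| Visit 6 | Days used | OLE start | Call, days after start | Visit 7, days after start |
|---|---|---|---|---|
| Day 83 | 0 | Day 83 | +14 | +16 to +26 |
| Day 90 | 0 | Day 90 | +7 | +9 to +19 |
| Day 90 | 7 | Day 97 | 0 | +2 to +12 |
| Day 97 | 0 | Day 97 | 0 | +2 to +12 |
| Day 97 | 7 | Day 104 | −7 | +1 to +5 (only Days 105 to 109 follow the start) |

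With Visit 6 exactly on Day 90, the call falls 7 to 0 days after the start. A call before the start needs v + d > 97. Since d is at most 7, this requires v ≥ 91.

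These offsets count from the OLE start. The first open-label application cannot be earlier than that and has no fixed date, so the interval from first application to call can be shorter still.

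**Double-blind comparison.** First application on Day 1. Call at 7 − 1 = 6 days for every subject called as scheduled. Visit 3 at (14 ± 5) − 1 = 8 to 18 days. The OLE matches this pattern closely only when the start is on Day 90.

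**The case against.** The case for leaving the schedule alone has substance. Day 90 is named as the first OLE visit, and on that date the call falls at +7 and Visit 7 at +14. Subjects hear about the OLE at Day 30, Day 45 and Day 60, so the 7 days may be a backstop that few use; the documents give no frequency. A late decider still has contact with the site at entry, with instruction and a diary. Section 10 asks for reasonable effort on timing, unscheduled visits are allowed, and Section 5.3 extends the safety board's remit to the OLE. No inferential analysis is planned for OLE efficacy or safety. All of this stands and limits the size of the point. None of it gives the Day 97 call any exposure to assess in a subject who starts on or after that day.

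A reader might go further and infer that Visit 7 can also fall before the OLE start, because its window opens on Day 99 and the latest start is Day 104. The documents do not support that. Section 10.2.4.2 requires returned tubes to be collected and weighed and the diary reviewed, which cannot be done before either has been issued. A date inside the window and after the start always exists.

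The objection about version also stands. The file holds the statistics section and appendices of a later version, whose own Tables 2-1 and 2-2 and Section 10.2.4 are absent. Its COVID-19 appendix refers telephone visits back to those tables. Nothing shown overrides the Day 97 call, but whether it was corrected cannot be checked.

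**Conclusion.** The point holds as a small safety-timing weakness in Amendment 2. The call can fall on the start day with Visit 6 exactly on time, and up to 7 days before the start with a late in-window Visit 6. What is lost is one telephone check for early local reactions, in those former vehicle and 100 µg/g subjects who start late.

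It would be wrong to infer that late starters go unmonitored. For a Day 97 start there is a clinic visit 2 to 12 days later, and diaries, site contact, unscheduled visits and the dose-reduction and stopping rules all continue. The double-blind primary analysis is not touched.

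The arithmetic is certain for the schedule shown. The number of subjects affected is unknown, and so is whether the later version still has this feature. The change is worth making because it is cheap; it is not essential.

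**What to change.** Define OLE Day 1 as the first open-label application, and set the first call 7 days after it in Table 2-2 and Section 10.2.4.1.

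**Preferred: count every OLE visit from that date**, with present spacing and windows: Visit 7 at 14 ±5 days, Visit 8 at 30 ±7, second call at 44, Visit 9 at 60 ±7, Visit 10 at 90 ±7. No visits are added. The cost is relabelled visits and database windows, including the PK, laboratory and ECG visits, and a longer maximum. Taking the first application on the OLE start day:
- Start on Day 97: 97 + 90 + 14 = 201, and 35 + 201 = 236 days instead of 229.
- Start on Day 104 (latest Visit 6): 104 + 90 + 14 = 208, and 35 + 208 = 243 days.

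**Minimal: move only the call**, and hold Visit 7 after it within the existing Day 99 to 109 window. For a Day 97 start, the call is on Day 104 and Visit 7 on Day 105 to 109. This works while s + 7 < 109, that is, for starts up to Day 101. For later starts the call interval must be shortened; a Day 104 start allows at most 4 days (call by Day 108, Visit 7 on Day 109). Study length does not change.

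**Avoid re-anchoring only the call and Visit 7.** Visit 8 would stay at Day 113 to 127. Visit 7 would be on Day 106 to 116 for a Day 97 start, overlapping that window, and on Day 113 to 123 for a Day 104 start, wholly inside it.
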